| | Dose, Opioid formulation, number Source (DOSE tool), other analgesics | ALBP, CLBP | ALBP, CLBP | ALBP, CLBP | ALBP, CLBP | CLBP | |
| | Device usage | | ALBP, CLBP | ALBP, CLBP | ALBP, CLBP | CLBP | |
| Sample Size | To estimate the M-Stim | interventi | on effect : | size, a retro | spective st | udy of | |
| | 59 cLBP patients on ch | ronic opioi | ds (100% | prolonged | opioid use) | | |
| | reported a 28% reducti | on in MME | after spin | al stimulat | or | | |
| | implantation,[40] reducing MME 26.2(SD32.8) compared to 5.8(SD34.2) | | | | | | |
| | for those with conventional treatment (effect size 0.60. A priori, we would | | | | | | |
| | be able to detect an effect size of 1 (meaning a difference of 1 standard | | | | | | |
| | deviation) with 94% power and alpha of .03 using a Wilcoxon Mann | | | | | | |
| | Whitney test with 30 in each group. With this effect size for a two-sided | | | | | | |
| | significance of 0.05, 17 participants per group would detect a 30% | | | | | | |
| | prescribing reduction, while 50 participants on chronic opioids per | | | | | | |
| | treatment group would provide 85.4% power to detect a 30% reduction in | | | | | | |
| | MME. Given the 20% in a previous study by Jamieson et al, we increased | | | | | | |
| | the cLBP sample to 50 | - | | Jannoson | icat, we iiio | ioasea | |
| | | | | | | | |

| | We planned to recruit 60 aLBP participants who had never taken opioids for their back pain, and 100 cLBP without a new prescription but with or without chronic opioid for cLBP. |
|----------------------------|--|
| Recruitment | Patients were recruited from Kaizo Health Centers in Landover and Fairfax, through direct referrals, flyers, and digital content like social posts and emails targeting local populations. Flyers were also distributed at three local pain clinics. |
| Randomization | After eligibility screening and informed consent, a 4-digit participant ID and the intervention allocation were randomly assigned by the survey software to either the DuoTherm or LG Smart TENS group within acute and chronic arms. A copy of the informed consent was emailed to the participant. |

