| Blinding (masking) | Participants were blinded to which device powered the study hypothesis, and blinded to their assigned intervention until after documenting initial NRS pain intensity. Success of blinding the study device (M-Stim) versus the active control (TENS) was tested at months 3-6 with prompts, "select which group you think you were in (control or treatment)" and "How confident are you (0 = Least Confident 100 = Most Confident)." The protocol statistician and study coordinator knew the intervention assignments during enrollment but did not conduct statistical analysis. The PI and treating chiropractor were blinded to allocation during enrollment, with the PI accessing data only after study completion. The analyzing statistician was blinded to device assignment until completion of data cleaning and initial analysis. |
| Data Collection Methods | Site coordinators entered identification and contact information after informed consent on a tablet, then recorded weight, height, and duration to confirm acute or chronic follow-up duration, then participants took the tablet to record pain intensity on a 0-10 NRS now and past 24 hours. While using the device for 30 minutes, participants completed 7-day pain intensity NRS, NIH Back Pain Research Minimum Dataset, including PROMIS measures of Physical Function, Pain Interference, Depression, and Catastrophizing via the Sullivan Catastrophizing scale, Injury Mechanism, prior treatments, exercise and athletic status. |
| | Participants were prompted to record analgesic use, pain, and device use daily for a month on the web-based platform, then weekly, with the monthly surveys adding Pain Interference. All surveys asked about |

analgesic use. Due to the anticipated heterogeneity of opioid formulations, a skip-logic data collection instrument algorithm was created with robust options for Dose per pill (34), Opioid formulations, e.g. hydrocodone, hydromorphone etc. (15) and the Source (DOSE tool, Supplement 2). Sources included "prescribed to me for this event", "prescribed to me for another event", "given to me by a family member", "given to me by a friend", "given to me by an acquaintance or stranger", or "purchased from someone without a prescription". These were converted to a total milligram morphine equivalent (MME) for analysis.

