Participants recorded when they used their device, duration of use, and any additional pain relief modalities (exercise, stretching, bath, hot tub, therapy, massage). Patients were asked to record any thermal use or therapy cycle or channel as appropriate to their device.

Participants verbally endorsing pain for less than three months (acute) were entered into a 3 month follow-up program, or 6 months (chronic) for those for whom back pain had been an ongoing problem for more than 3 months.

Statistical Methods

Statistical analysis was performed with masked intervention allocation by a statistician new to the project to determine differences in primary and secondary outcomes.

An intention-to-treat analysis included all participants meeting inclusion criteria. Summary statistics (means, standard deviations, proportions) were calculated using T-tests and Chi-squared tests. Opioid prescribing differences were calculated with raw percent of change and relative risks. Diary entries and item-level data were analyzed for missing data to assess the need for imputation. Relative risks were calculated for MME and opioid use days between intervention groups, with paired T-tests used to compare first two and last two weeks of MME in those who used opioids during the study. A linear regression assessed BMI's interaction with opioid use, calculating marginal effects with standard errors via the Delta Method. Data analysis was performed using STATANow/SE 18.5.

For pain outcomes, in addition to the above methods, missing 10 day NRS-1 data will be imputed using forward fill and KNN. A neural network will be created to determine factors contributing to 13 week Pain Interference, with iterative modeling to reduce mean absolute error. Graphs with r-squared for predictors will be generated.

| Data Monitoring | Data collection was conducted through an app that tracked daily pain, opioid use and device usage. Monitoring included weekly enrollment review by the protocol statistician to assess comprehension of the data collection tool. Adverse events were reported as per protocol. | |
|------------------------|---|--|

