monthly surveys added past month NRS, Blinding assessment for additional 3 months for those started in chronic strata. Added "source" for each opioid use case to DOSE tool collecting opioid formulation, dose, and number of pills. We intended to use evaluate change in MME over time for chronic opioid users. The FDA recommended requiring participants on opioids maintain dosage and frequency. As we did not have access to prescribing records, and opioid reduction was a desired outcome measure, we evaluated opioid use for the first two weeks versus the last two of those endorsing prior opioid use. We extended the baseline and follow-up Pain Intensity measurements to one month rather than one week. 3a) 8/31/22 – Site Visit. PI noted staff using "will not fit" criteria rather than BMI of 30 from pilot study. New device fits variable BMI, based on abdominal girth. Retained "if device fits", exclusion criteria using BMI changed to BMI >50, noting controversy in using BMI as exclusion criteria. 4) 5/5/23; Added "Do you think you will need surgery" and "do you think you will need epidural" questions, and "did you get surgery" and "did you get an epidural" to monthly. 5) 7/13/2023 New Location added Stratification by chronicity versus opioid use status: enrollment strata were based on verbal endorsement of duration and no acute opioid use for back pain. Initial evaluation of registration data after enrollment was complete revealed 16 of 60 in the "acute" strata reported a duration longer than three months, and half in each chronicity strata no prior opioids for LBP. In consultation with Clinical Trials.gov, we pooled the data and included both opioid and pain outcomes as a single NCT04491175 registry with two different publications and analyses. Informed Informed consent will be obtained from each participant after screening. Consent Participants will be informed about the voluntary nature of the study, with a HIPAA form for confidentiality. Consent will be documented via selecting 'continue' on the digital consent form. Confidentiality Patient data will be stored on password-protected network drives. All data will be de-identified using a unique study ID for each participant. Confidential records will be stored in secure, restricted-access rooms. Declaration of The principal investigator has financial conflict of interest from design interests and research into the DuoTherm device, and creating a company to

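### The neural network for 13-week Pain Interference is iterated to lower its error and reported by r-squared, on at most 160 participants, with no validation described

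*Combined protocol and SAP*

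**What the plan says.** The combined protocol and SAP gives this analysis two sentences, at the end of Statistical Methods: "A neural network will be created to determine factors contributing to 13 week Pain Interference, with iterative modeling to reduce mean absolute error" and "Graphs with r-squared for predictors will be generated". The only modelling aim stated is a smaller mean absolute error (MAE).

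The documents do not say on which data the MAE or the r-squared is computed. They give no training and test split, cross-validation, penalty or early stopping. They also give no architecture, predictor list, end point for the iterations, or criterion for counting a variable as a contributing factor.

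On missing data, the only method named for pain outcomes concerns a different variable: "missing 10 day NRS-1 data will be imputed using forward fill and KNN". The section otherwise says only that missing entries were examined to see whether imputation was needed. The number with 13-week Pain Interference may therefore fall below the number randomised.

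**The concern.** A flexible model that is revised repeatedly to lower its error will fit chance patterns when there are few outcomes and many candidate inputs. If the error that guides the revisions comes from the data used for fitting, or from one validation set used again and again, the r-squared reported afterwards is too high. The variables that the model relies on can then look like predictors when they are not.

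What is at stake is the credibility of any predictors named in the pain publication. Pain Interference is also the scale of the chronic-pain primary outcome, at 6 months, so readers may give such findings weight. The plan does not label the analysis exploratory.

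**Working it through.** **Inputs**
- Participants (Sample Size): "We planned to recruit 60 aLBP participants who had never taken opioids for their back pain, and 100 cLBP without a new prescription", so 60 + 100 = 160. Under Protocol Amendments the strata were combined: "we pooled the data and included both opioid and pain outcomes as a single NCT04491175 registry with two different publications and analyses". All 160 could therefore enter one model. As a lower case I take n = 100, which is the chronic stratum alone, or the pooled set with 60/160 = 37.5% missing at 13 weeks (assumption).
- Predictors: number not stated. Data Collection Methods lists baseline measures "including PROMIS measures of Physical Function, Pain Interference, Depression, and Catastrophizing via the Sullivan Catastrophizing scale, Injury Mechanism, prior treatments, exercise and athletic status", and device use and analgesic records are also collected. Assumed p = 10, 20 or 40.
- Network: not stated. Assumed one hidden layer of h = 4, 8 or 16 units, which has p·h + 2h + 1 weights.

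**1. The plan's own figure.** There is none for the network. The power behind the 100 chronic participants can be checked. The effect size is d = (26.2 − 5.8)/√[(32.8² + 34.2²)/2] = 20.4/33.5 = 0.609. With 50 per group, a two-sided t-test at 0.05 has 85.4% power, as stated. That figure concerns morphine equivalents and says nothing about whether 160 is enough for this model.

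**2. Fit computed on the fitting data.** Predictors and outcome were simulated as unrelated noise. Networks were trained on absolute error, with 15 replicates per setting and 2000 new cases. R² = 1 − SSE/SST.

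| p | h | weights | n=160: R² in-sample | n=160: R² new | n=100: R² in-sample | n=100: R² new |
|---|---|---|---|---|---|---|
| 10 | 4 | 49 | 0.35 | −0.82 | 0.55 | −1.17 |
| 10 | 8 | 97 | 0.69 | −1.47 | 0.91 | −2.15 |
| 10 | 16 | 193 | 0.99 | −2.14 | 1.00 | −1.20 |
| 20 | 4 | 89 | 0.65 | −1.38 | 0.87 | −1.89 |
| 20 | 8 | 177 | 0.99 | −2.28 | 1.00 | −1.31 |
| 20 | 16 | 353 | 1.00 | −0.87 | 1.00 | −0.69 |
| 40 | 4 | 169 | 0.95 | −2.24 | 0.98 | −1.90 |
| 40 | 8 | 337 | 1.00 | −1.27 | 1.00 | −1.29 |
| 40 | 16 | 673 | 1.00 | −0.67 | 1.00 | −0.86 |

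In-sample MAE was 0.01 to 0.51 SD. Predicting the centre for everyone gives √(2/π) = 0.80 SD. On new cases the networks did worse than that, at 1.02 to 1.44 SD. For comparison, ordinary linear regression on noise has expected R² = p/(n − 1), which is 10/159 = 0.06 to 40/159 = 0.25 at n = 160.

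A separate run with 20 noise predictors, a light ridge penalty (1e-4) and 3, 5 or 10 units (67, 111 or 221 weights) gave 0.63, 0.89 and 1.00 at n = 160, again negative on new data. With a much stronger penalty the in-sample values were still 0.51 to 0.74.

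**3. Tuning on one reused split.** With 20 noise predictors, 20% was held back (32 of 160, or 20 of 100) and the candidate with the smallest MAE on that split was kept. Mean squared correlation on the split:

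| models tried | n=160 | n=100 |
|---|---|---|
| 1 | 0.03 | 0.05 |
| 10 | 0.05 | 0.09 |
| 50 | 0.10 | 0.14 |
| 200 | 0.12 | 0.19 |

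On fresh data it was about 0.001 throughout. Measured as 1 − SSE/SST, the values after 200 models are 0.06 and 0.11.

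**4. One r-squared per predictor.** The largest single-predictor r² under noise averages 0.024, 0.031 and 0.038 for p = 10, 20 and 40 at n = 160, and 0.038, 0.048 and 0.060 at n = 100. The chance that at least one independent predictor reaches p < 0.05 is 1 − 0.95^p, which is 40%, 64% and 87%.

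**The case against.** The strongest reply is that the plan is silent on validation and does not exclude it. Lowering MAE by iteration is compatible with tuning by cross-validation and reporting on untouched data. That stands: a reader might infer that the plan holds nothing out and must therefore report noise as signal, but the text says neither. The inflation is conditional on how the unstated steps are done. Silence is still not harmless, because the one aim that is stated gives optimistic results on fitting data and, more weakly, on a reused split.

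Second, the wording about the graphs may well mean one r-squared per predictor. That reading is natural, and under it the high whole-model values do not apply. What remains is the multiplicity in step 4.

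Third, the simulations lean towards a bad case: every predictor is noise and penalties are mostly negligible. Real data will hold some signal, so these figures show how much fit can arise with no signal at all. They do not forecast the trial's r-squared. Nor does the argument need more weights than participants: several of the networks above have fewer than 160.

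Fourth, a reader might take this for the plan's only analysis of who benefits from the device. It is not. As described, the network models the outcome and not a treatment effect. The plan also has a BMI interaction regression, and secondary outcomes in participants with more severe pain or higher Pain Interference.

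**Conclusion.** The concern holds in conditional form and is minor. As described, the analysis cannot show that any factor predicts 13-week Pain Interference, because nothing separates fitting and tuning from assessment.

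- Whole-model r-squared on fitting data: 0.35 to 1.00 from noise at n = 160, and 0.55 to 1.00 at n = 100.
- One split reused for tuning: squared correlation of about 0.1 to 0.2 after 50 to 200 tried models.
- One r-squared per predictor: only about 0.02 to 0.06 for the best, but a 40% to 87% chance of at least one nominally significant factor.

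These sizes rest on assumed numbers of predictors, hidden units and analysed participants. The last also assumes independent predictors and a 0.05 criterion, which the plan does not state. With nested validation or an untouched test set the problem would not arise.

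It would be wrong to infer that the trial's main results are threatened. The network is not listed among the primary or secondary outcomes and enters no primary treatment comparison.

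**What to change.** Before the model is fitted, add a short paragraph to Statistical Methods that:

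- fixes the candidate predictors, including whether measures taken after randomisation, such as device use, are allowed;
- fixes the tuning grid, and states how missing 13-week values are handled;
- runs all tuning and predictor selection inside nested cross-validation;
- reports only out-of-fold MAE and r-squared, and says whether r-squared refers to the whole model or to single predictors;
- sets these beside a model with baseline Pain Interference alone, or a penalised linear model, fitted and assessed in the same way;
- presents any named factors as hypothesis-generating.

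If the network has already been fitted, the same procedure can be rerun on the existing data and reported as post hoc. No new data are needed. The cost is a little more analysis work and a lower reported r-squared. If only the minimum is wanted, it is to state on which data MAE and r-squared are computed and to keep those data out of every tuning step.

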| | Participants will be instructed to use the device for a minimum of 30 minutes a day. Both M-Stim and LG Smart TENS groups will receive a standard pain management regimen typically used for low back pain standardized across all clinicians participating in the study. Participants will keep the devices and be instructed to use them for pain as needed during the duration of the study. |
| Outcomes | Opioid Use Primary Outcome: |
| | Prior use: For patients with prior or ongoing opioid use, a 30% reduction in MME (Milligram Morphine Equivalents) between the first 14 days and the last 14 days of daily diary recordings using the DOSE data collection tool. |
| | Opioid naïve: 30% reduction of those receiving an opioid prescription "prescribed to me for this event" |
| | Secondary outcomes: Use days; total MME and use past 7 days in the opioid naïve; use days by those with more severe pain using the NIH Research Taskforce definitions; and prescribing compared to a contemporaneous national LBP population (25%). |
| | Pain Primary Outcome: |
| | Chronic: 30% lower disability at 6 months using PROMIS Pain Interference for those with ongoing pain >3 months |
| | Acute: 30% lower NRS 0-10 "pain now" from entry to 10 days for those presenting with an episode of pain starting within the past 2 weeks |
| | Secondary Outcomes: Change in disability for those with >=57.7 PROMIS Pain Interference; restoration of function to normal (PI=50); |

| | integrated analysis with | n common | criteria fo | r restoration | on of function | on with | |
|-------------------------|---|---------------|--------------------|---------------------|----------------------|----------------------------|--|
| | multifidus stimulation s | surgery. | | | | | |
| | | | | | | | |
| Participant Timeline | | Initial Visit | Daily x 28 days | Weekly for 3 months | Monthly for 3 months | Monthly 4 - 6 months | |
| | Consent, Enrollment, Randomization | ALBP, CLBP | | | | | |
| | Minimum Dataset, Pain Catastrophizing Sullivan, PROMIS Depression, Physical Function | ALBP, CLBP | | | | | |
| | NRS (at that moment & past 24 hours) | ALBP, CLBP | ALBP, CLBP | ALBP, CLBP | ALBP, CLBP | CLBP | |
| | NRS after 30 minutes | ALBP, CLBP | | | | | |
| | NRS Past week | | | ALBP, CLBP | ALBP, CLBP | CLBP | |
| | NRS Past month | | | | ALBP, CLBP | CLBP | |
| | PROMIS Pain Intensity, Pain Interference | ALBP, CLBP | | ALBP, CLBP | ALBP, CLBP | CLBP | |

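### After pooling, the chronic 6-month co-primary population is not fixed: its literal wording takes in 16 acute-stratum participants with no month-6 measure scheduled, and no listed analysis uses the randomisation stratum

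*Combined protocol and SAP*

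**What the plan says.** **Allocation and follow-up.** The Randomization section has the survey software allocate DuoTherm or TENS separately within acute and chronic arms. Protocol Amendments explains how people reached those arms: "enrollment strata were based on verbal endorsement of duration and no acute opioid use for back pain". Data Collection Methods ties follow-up to the same verbal report: "Participants verbally endorsing pain for less than three months (acute) were entered into a 3 month follow-up program", with six months for those whose pain had lasted longer. In the Participant Timeline, Pain Interference in months 4 to 6 is scheduled for CLBP only.

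**Co-primary pain outcomes.** The Outcomes section gives "Chronic: 30% lower disability at 6 months using PROMIS Pain Interference for those with ongoing pain >3 months". The acute co-primary is the 10-day NRS in those whose episode began in the previous two weeks.

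**What was found later.** The closing note of Protocol Amendments reports that 16 of 60 in the acute "strata reported a duration longer than three months, and half in each chronicity strata no prior opioids for LBP". The response was that "we pooled the data and included both opioid and pain outcomes as a single" registry record, with two publications.

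**Analysis.** Statistical Methods lists t-tests, chi-squared tests, relative risks, paired t-tests and a regression on BMI; none is described as using stratum. The intention-to-treat set is everyone who met the inclusion criteria, and no separate population is given for each co-primary. Missing data were to be examined for a possible need to impute, but the only pain imputation specified is for the 10-day NRS.

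**The concern.** Two possible classification variables now exist, the stratum at randomisation and the reported duration, and they disagree for more than a quarter of the acute stratum. The chronic co-primary is worded by duration, while the data needed for it were scheduled by stratum. An analyst who follows the wording literally after pooling builds a 6-month set in which some members have no month-6 value by design, with no stated rule for them. Leaving those values missing and filling them in from month 3 are different analyses of a co-primary endpoint, and the choice would be made after enrolment had closed.

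Separately, pooled comparisons that omit stratum do not follow the way the trial was randomised. This bears on the opioid outcomes. With half of each stratum reporting no prior opioids, both the opioid-naïve and the prior-use comparisons draw on both strata.

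**Working it through.** **1. The plan's own figure.** No power is stated for 6-month Pain Interference. The nearest figure, in Sample Size, is 85.4% with 50 per group for MME.
- Effect size: d = (26.2 − 5.8)/√((32.8² + 34.2²)/2) = 20.4/33.51 = 0.609 (the plan gives 0.60).
- Two-sample t-test, two-sided 0.05, n = 50 per group: noncentrality d√(n/2) = 0.609 × 5 = 3.04 on 98 df, power 85.4%.

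The figure reproduces. It concerns MME and is not affected by this point.

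**2. The counts.** Inputs are 16 and 60 from Protocol Amendments, and the planned 60 and 100 from Sample Size.
- Share of the acute stratum: 16/60 = 26.7%. This needs no assumption.
- Share of a duration-defined 6-month set: 16/(100 + 16) = 16/116 = 13.8%. This assumes 100 enrolled in the chronic stratum, all reporting more than three months.
- Share of all planned participants: 16/160 = 10%.

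**3. Who can have a month-6 value.** By stratum, the set is 100, all scheduled for month 6. By reported duration it is 116, of whom 100 are scheduled. A complete-case analysis of the 116 therefore falls back to the same 100 (before other dropout). The two definitions give different month-6 results only if values are filled in for the 16, or if the 16 enter a longitudinal model through their data up to month 3.

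**4. Illustration of filling in.** This borrows d = 0.60 from MME, since no Pain Interference effect size is given, and assumes 1:1 allocation and no other dropout. Let f be the fraction of the effect carried by the filled-in values. The average effect over 116 is then 0.60 × (100 + 16f)/116, with 58 per group.

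| Set | Effect | Power |
|---|---|---|
| 100, by stratum | 0.600 | 84.4% |
| 116, f = 0 | 0.517 | 78.9% |
| 116, f = 0.5 | 0.559 | 84.7% |
| 116, f = 1 | 0.600 | 89.3% |

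The rows for 116 count filled-in values as if observed, so they show only that the choice matters. They do not forecast this trial.

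**5. Strata within the opioid comparisons.** At planned enrolment, half of each stratum without prior opioids is 60/2 = 30 acute and 100/2 = 50 chronic, a pooled opioid-naïve group of about 80. The prior-use group has the same make-up.

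**The case against.** The strongest reply is that the 6-month population was never in doubt. The Outcomes wording closely matches the Data Collection Methods rule that sends people to six months of follow-up, the timeline schedules months 4 to 6 for CLBP only, and a 6-month outcome most naturally means the people followed for six months. The pooling sentence concerns the registry record and publications and does not redefine any population. This stands to the following extent: a reader might infer that the 16 were moved into the 6-month analysis, and the documents do not say so. It does not settle the matter, because the acute co-primary in the same section is defined by episode onset and not by the whole acute stratum, and nothing after the pooling sends the analyst back to the strata.

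Three other inferences are tempting and not supported:
- *That the 16 have no usable primary pain outcome.* The two-week limit concerns the episode. Someone with long-standing pain and a recent flare could meet it, and episode onset for the 16 is not given.
- *That dropping the 16 changes the 6-month result.* Step 3 of the working shows that complete-case analysis returns the chronic stratum.
- *That the standard errors are wrong.* No blocking within stratum is described, and no error in the unadjusted standard errors is shown. In a chronic-stratum analysis stratum is constant, so the term is relevant only to pooled comparisons.

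It is also fair to say that reported duration is a baseline characteristic, so classifying by it does not in itself break the randomised comparison. However, the documents do not say which record showed the longer duration, or whether it was made before assignment. Staff recorded duration at entry, while the Minimum Dataset was completed during device use.

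**Conclusion.** The point holds as a gap in the definition of a co-primary population, together with unstratified pooled analyses of a trial randomised within strata. Sixteen of 60 acute-stratum participants (26.7%) fit the literal wording of the chronic co-primary but had no Pain Interference measure scheduled after month 3. Whether they were included is not stated. If they were, they would make up 13.8% of the set, on the assumption that the planned 100 chronic participants were enrolled and all report more than three months. Actual chronic enrolment, the number in that stratum reporting a shorter duration, and the split of the 16 by device are not given, so no bias in the treatment effect can be calculated. Fixing the set by stratum is the safer choice, because stratum was assigned before allocation and matches the follow-up schedule. The gain from a stratum term in pooled comparisons is precision and consistency with the randomisation. It does not correct a demonstrated error.

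**What to change.** 1. Define the 6-month Pain Interference co-primary population as those randomised in the chronic stratum, and state that no month-6 values are imputed for the acute stratum.
2. Keep the acute co-primary's two-week episode-onset restriction and apply it within the acute stratum.
3. Include randomisation stratum as a factor in every pooled treatment comparison, opioid outcomes included. For prescribing, this can be a stratum-adjusted relative risk; for MME change, a between-device comparison with a stratum term.
4. Add a sensitivity analysis of the chronic outcome by reported duration, in which the 16 contribute only their Pain Interference data up to month 3.
5. Report the cross-tabulation of stratum by reported duration and device, and say when the reported duration was recorded.

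The cost is SAP wording, one model term and one sensitivity analysis. No new data are needed.
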